# 1. Background

Sickle cell disease (SCD) is a genetic disorder of red blood cells. The abnormal sickleshaped cells become trapped in the circulation creating blockages, often triggered by infections. Around 50% of deaths in the under-5s with SCD are due to infection. Blockages of blood vessels by sickle cells is associated with sudden episodes of severe, intractable pain particularly affecting the bones. A complex sequence of events follows which culminates in organ damage so that later in life SCD patients experience failure of the heart, lungs, brain, kidneys and other organs. SCD detrimentally affects growth and intellectual development which, coupled with unpredictable episodes of pain and hospitalisations, impacts on schooling, employment and mental health. For SCD patients, each life stage childhood, adolescence, adulthood—brings its own challenges.

The World Health Organization (WHO) has declared SCD a public health priority; 75% of the 300,000 annual global SCD births occur in Sub-Saharan Africa (SSA). Although accurate data are lacking, around 6 million Africans are living with SCD and 50–80% will die before adulthood, predominantly in the first 5 years of life. The vast majority of patients in SSA with SCD are never diagnosed so addressing this inequity is key to achieving the SDGs "Leave No One Behind" agenda and WHO's revamped commitment to Universal Health Coverage. WHO estimates that 70% of SCD deaths are preventable with: a) appropriate clinical management (see below); b) early identification of SCD; and c) patient-centred care. The introduction of such interventions have enabled high-income countries to reduce SCD deaths from 3 to 0.13 per 100 person years of observation. This means up to 94% survive to 18 years in the USA and 99% to 20 years in the UK. Our research will focus on these aspects of SCD care.

#### 1.1 Clinical mainstays for SCD

**Penicillin prophylaxis:** People with SCD are particularly susceptible to infections, especially of the respiratory tract and blood (i.e. septicaemia). This is partly because their spleens are damaged by the sickle-shaped red blood cells and splenic function is important for the immune system to clear infections. Lifelong antibiotic prophylaxis is therefore recommended for all people with SCD. Though the benefits in adults are equivocal, it is particularly important that there is full adherence to prophylactic penicillin up to 5 years of age. A Cochrane systematic review of three randomized trials (n = 857) assessed the effects of prophylactic antibiotics for preventing pneumococcal infection in children with SCD. It concluded that prophylactic penicillin significantly reduces the risk of pneumococcal infection in children with SCD <5 years of age, and is associated with minimal adverse effects. Penicillin prophylaxis should start by 3 months of age (recommended doses are: for children <1 year, 62.5 mg twice a day; children aged 1–5 years, 125 mg twice a day; for adults and children >5 years of age, 250 mg twice a day). If the person is allergic to penicillin, oral erythromycin should be given. Standards and guidelines recommend that 90% of infants should have been offered and prescribed penicillin (or alternative) by 3 months and 99% by 6 months. It is important to start by 3 months of age, as this is when the level of semiprotective foetal haemoglobin (HbF) starts to decline and the risk of splenic hypofunction increases. Although not the main focus of our research, vaccinations against infections (e.g. pneumococcus, influenza, meningitis, hepatitis B, papilloma virus - adults only) are also recommended for SCD patients.

*Hydroxyurea (also known as hydroxycarbamide)* reduces anaemia in SCD, increases haemoglobin levels (which improve the oxygen-carrying capacity of the blood), reduces anaemia, lessens blood transfusion requirement and reduces mortality. It also reduces the 'stickiness' of red cells thereby improving blood flow, though its maximal effect may take several months. In a randomised control trial it reduced mortality by 40% after 9 years and in a non-randomised study from Greece, the probability of 10-year survival was 86% for those on hydroxyurea, compared with 65% for those not on hydroxyurea even though the treated group had more severe disease. Hydroxyurea also reduces painful episodes and chest crises, and reduces pain, transfusions, hospitalisations and hospital stay in children and young adults with SCD. It can be used as an alternative to transfusions in stroke prevention. The use of hydroxyurea translates into public health cost benefits. It has clinical value at all ages, even in asymptomatic young children, and guidelines advise it should be offered to all children, even those with no symptoms. It is well tolerated with few side effects and no chromosome damage (i.e. no risk of mutagenicity or carcinogenicity).

**Blood transfusion** is recommended in SCD for strokes, acute chest syndrome and perioperatively. Blood transfusion is life-saving for acute complications or to prevent the development or progression of chronic complications. The major goals of transfusion in SCD are to (i) improve oxygen-carrying capacity by correcting anaemia and (ii) prevent or reverse complications of SCD-related blood vessel blockages and red cell breakdown. It can be given either as a top-up (as in routine transfusions) or exchange transfusion (to replace simultaneously-removed patient's sickle cell blood). Complications of transfusion in SCD include allo-immunisation, iron overload, haemolytic transfusion reactions and transfusiontransmitted infections. Ideally all SCD patients should be immunised against hepatitis B whether or not they are on regular transfusions and annual testing should be undertaken for transfusion-transmitted viruses for recipients of transfusions.

The decision to transfuse a patient with SCD must be taken by a trained clinician with expertise in managing patients with SCD because they need to consider the degree of anaemia relative to the patient's steady state haemoglobin concentration and overall clinical condition. In high income countries all SCD patients must have extended red cell antigen typing performed to prevent the development of antibodies after transfusion. However, such typing is not widely available in SSA. In SSA, shortages of blood and facilities able to provide a transfusion, mistrust of the health system, lack of understanding about blood donation and the transfusion process, and poor uptake of care mean that when blood is available it is mostly used in SCD for treatment of acute anaemia.

#### 1.2 The unmet needs and gaps our study will address

Improving early detection and uptake of care, use of the clinical mainstays for SCD, and patient-centred care will be the focus of our research, as these three areas constrain SCD care in SSA, exacerbating morbidity and mortality.

**Poor early detection and uptake of care:** Failure to diagnose SCD means it is very difficult to provide evidence about the burden and gravity of problem to policy makers so they can implement appropriate programmes. At least 50% of individuals with SCD in SSA are never diagnosed and therefore do not take up care. For example, Nigeria's SCD prevalence is ~4 million among its population of 202 million; only ~30,000 patients (<1%) are registered in health facilities (co-principal investigator ([name]) personal communication).

Consequently, there are very limited data from SSA on morbidity and mortality. In Tanzania, the average life expectancy of SCD patients managed in high-quality facilities is 33 years compared to 52 years among their national healthy peers. The overall mortality rate of 1,725 SCD patients in Tanzania from 2004 to 2009 was 1.9/100 person years of observation and was highest in those under 5-years old (7.3/100 person years). In Nigeria SCD accounts for 5.6% of national under-five mortality. **These deaths rates are similar to those in high-income countries prior to the routine implementation of clinical mainstays for SCD**.

**Inadequate clinical management and continuity of care:** In addition to poor implementation of clinical interventions for SCD that are known to work there are particular failures in health service delivery for SCD patients so they are marginalised and 'left behind'. These are: failure to identify most babies born with SCD; a potentially difficult transition for adolescents from paediatric to adult clinics; and emphasis on crisis management rather than chronic, preventative care. Deriving solutions from high-income country contexts and attempting to apply them in SSA in a 'one size fits all' approach is not likely to work because of the nuances of local culture and context, and the scale of the problem in SSA. To navigate this complexity, our research puts the perspective and voices of SCD patients (working together with healthcare providers) at the heart of all our activities, actively involving them in identifying local, context-specific problems linked to the clinical mainstays and in implementing solutions.

Lack of patient-centredness: The traditional focus on management of SCD from a clinical perspective has dominated SCD care resulting in lost opportunities to understand, respond to and mitigate barriers (e.g. education, economics, geography) that limit access, uptake and adherence to clinical care. Lack of patient-centredness means health care services do not span the continuum of care and the life-course of patients. Patient-centred care sees health care as a partnership between providers and users. It facilitates provision of care that engages patients in defining what is appropriate, accessible and of good quality, and in health providers being responsive to this.

# 2. Purpose of the Research

There is a clear need to improve early detection and uptake of SCD, to increase use of clinical mainstays, and, throughout, to provide care that is patient-centred. To do so, we will deploy participatory approaches in order to drive both supply- and demand-side factors affecting each of these three components. We will then study implementation and outcomes of these approaches with the overall aim of influencing policy and practice for SCD in our three study contexts: Ghana, Nigeria, Zambia.

Within each country, we will work with six health facilities with known SCD care provision. In these facilities we will identify a team of healthcare providers with responsibility around SCD care. We will also work with a community group from within the catchment area of each health facility. This group will be comprised of (adolescent/adult) individuals with SCD, carers of patients with SCD, and community influencers.

The **community group** will use **participatory action cycles** (PACs) in order to drive community sensitisation around SCD to improve earlier detection and uptake of care, and also to overcome access barriers. The **facility group** will carry out **standards-based audit** 

(SBA) in order to drive uptake of the clinical mainstays and also to promote earlier detection of SCD in newborns, which facilitates earlier uptake of clinical mainstays for reduced morbidity and mortality (see section 3.5 on recruitment of both of these teams). The facility and community groups will come together in order to co-develop a model for patient-centred SCD care in **learning collaboratives**, which should be reflected in the care provided at each facility. From this combination of activities, we draw our overall study title: Patient-centred management of sickle cell disease in Africa (**PACTS**).

#### 2.1 PACs implementation (months 18–42)

PACs follow *plan-act-observe-reflect cycles*. Each PAC team will **identify key barriers** to early identification (e.g. due to gaps in local knowledge) and uptake of SCD care. Teams will rank the barriers and **plan** which barriers would be feasible and impactful and which to tackle first. They will then brainstorm possible solutions, agree on one and enumerate local assets and resources that need to be mobilised to implement the solution. These will not be provided through the project since that would undermine sustainability and ownership. All the PACs teams will implement their chosen solution over 2-3 months (**'act'**) and then appraise (**'observe'**) whether the solution has worked or if it needs adjusting. They will **reflect** on the overall strengths and weaknesses of their approach, evaluate the impact, and determine whether to adapt, adopt (embed), or abandon their approach, determining next steps needed. Finally, they will, after an approach has been determined to be successful and has been embedded, identify the next barrier they will address in a new cycle.

#### 2.2 SBA implementation

SBA teams will be established and healthcare and transfusion providers will be orientated about its steps. Like PACs, it is a cyclical problem-solving approach. It begins with identifying a specific standard of care to uphold (e.g. penicillin prophylaxis for children, hydroxyurea maintenance, guidelines for transfusion in SCD). They then collect a baseline measurement of performance against that standard, carrying out a root cause analysis to understand why the standard is not being met and identify and implement a solution to tackle root causes. A second measurement is then taken after approximately 2–3 months to determine if improvements have been made and to reflect on why (or why not) and to adjust the solution if needed.

Overall, each cycle will sequentially address priority barriers (8-12 barriers each per PACs and SBA team). In total, up to 48-72 patient/carer/community solutions (to overcome access constraints to patient-centred care) and up to 48-72 clinician-generated solutions (to implementing evidence-based standards for SCD care) will be tested, refined and adopted. Where teams across countries are tackling similar barriers, we may establish WhatsApp groups or Teams check-in meetings to foster cross-country learning.

PAC and SBA teams will be supported by a PACTS study SBA and PAC lead. A research coordinator in each country will offer logistical support to these leads. These individuals will support the formation of each team, capacity strengthening to use each approach, and will carry out intensive monthly **mentoring and coaching** to help teams overcome any implementation challenges they may be facing and to facilitate continuous learning opportunities. PhD students may support some implementation, but will largely be

responsible for carrying out independent study of different aspects of the intervention, which will be determined by them, but aligning with the priorities of each country study team.

#### 2.3 PAC and SBA learning collaboratives

Each country PAC and SBA team will meet monthly. The SBA and PAC leads (with support from PhD students in our PACTS research consortium) will facilitate larger collaborative meetings every three months for all PACs and SBA teams associated with each health facility to come together. *In addition, members from community-based organisations supporting SCD patients/carers of people living with SCD and higher-level stakeholders from blood services and the ministry of health will be invited to at least one learning collaborative each year.* 

Representatives from all PAC and SBA teams from the three partner countries will attend the biennial workshops. All these meetings will be used to reflect and for peer learning—to develop capacities and technical skills, to share good practices that might be adopted elsewhere, to help overcome common challenges using PACs and SBA, and to engage in "friendly competition". An additional central purpose of these learning collaboratives will be for community- and facility-based teams to work together to share their experiences to identify what **patient-centred SCD care** in each context entails and to collaboratively develop guidance for supporting patient-centredness in SCD care. Part of the SBA activities will then also entail moving this guidance into practice. We will learn about the practicality of these guidelines through the SBA activities and will refine them to ensure they are fit-for-purpose. We will promote their incorporation into national guidelines through dissemination activities throughout the life of the study.

Learning from these approaches around characteristics of patient-centred SCD care, barriers and facilitators of routine use of clinical mainstays, core constraints around early uptake of care and access to care more generally, key activities that can support improved access of SCD care, and approaches to broader community SCD sensitisation will be captured through intensive implementation research. Key insights will be collated and shared with policymakers with the aim of influencing policy improvements for patient-centred, evidence-based SCD care.

# 3. Methods

#### 3.1 Research Question, Aim, and Objectives

#### **Research Questions**

- i. Why are proven interventions for SCD that save lives in high-income countries not being widely used in SSA?
- ii. What, according to patients, carers and SCD healthcare providers, constitutes patient-centred SCD care?
- iii. What constraints do patients experience when trying to access proven interventions for SCD at different stages of their lives?
- iv. What solutions devised by patients and healthcare providers can advance patientcentred care and sustainably overcome constraints to both uptake of care and implementation of clinical mainstays?

#### Aim

To improve wellbeing and health outcomes for SCD patients in SSA through earlier and improved detection of SCD and optimised implementation of known evidence-based clinical interventions, using a patient-centred approach.

#### Objectives

- 1. To understand the barriers SCD patients face in accessing and adhering to care at different life stages.
- 2. Use participatory actions cycles (PACs) as platforms for SCD patients/carers and community members to together support community sensitisation for earlier uptake of SCD care and to overcome access barriers.
- 3. To work with SCD patients/carers, their communities, healthcare providers and policy makers to generate and implement guidelines for patient-centred SCD care .
- 4. To work with SCD patients/carers, their communities, healthcare providers and policy makers to consistently use successful patient-centred solutions and evidence-based SCD care.
- 5. Use a realist evaluation to explore barriers preventing a) uptake of SCD care, b) implementation of evidence-based practice, and c) patient-centred care in terms of what worked, for whom, under which conditions, and why.

#### 3.2 Study Design

To study implementation of the intervention in-depth, we will carry out a realist evaluation (see section 3.3 below). As this is implementation research, implementation of the intervention and study of the implementation process will occur simultaneously in a phased approach as detailed below. However, of note is that though PACs and SBA introduction, capacity-strengthening, and support to community and clinical teams is our intervention, they too can be considered as approaches to implementation research, generating rich insights around local barriers and how to overcome these, all of which will be captured.

In months 0–6, the study team will be established, staff members (PAC and SBA leads) hired and trained, and community entry established.

#### 3.3 Data Collection

**Phase 1:** Situational analysis; selection of facilities and PACs and SBA teams (months 7–18)

**Situational analysis:** The purpose of the situational analysis is familiarisation with current knowledge on: social factors affecting access to SCD care\*; patient/carer expectations of patient-centred care; and key barriers constraining implementation of evidence-based SCD clinical mainstays and adopting patient-centredness in care provision.

Information from **a** *scoping (literature, policy), and media review* summarising what is known about SCD and accuracy of public information (from the media review), and a *patient* 

\* Please note that this will be complemented by research into geographical and financial factors that are part of an epidemiological and mapping study (for which a separate ethics application will be submitted). This will be an ongoing study that will also be designed to detect changes in clinical mainstays and patient outcomes.

*survey* about barriers to accessing care will be used to brief the PACs and SBA research teams (see Phase 2). Additional information will be obtained from a *qualitative study*.

#### Scoping and media reviews

A scoping review involving peer-reviewed and grey literature (including policy and guidelines for SCD in each country and in SSA more broadly) will be conducted to synthesise current global knowledge about barriers to accessing and implementing SCD care in SSA and to collate current guidelines on SCD management. Public misperceptions about SCD that exacerbate stigma are common and can be countered by more sensitive and accurate reporting, so we will also undertake a review of media reports† (i.e. media content analysis) from 2019–2022 to identify trends and gaps in knowledge and possible opportunities for sensitisation. To enhance quality, these reviews will involve systematic identification of articles, independent extraction of data, and coding of data by two researchers with arbitration by a third researcher.

#### Baseline patient survey

Using information from the scoping review and media content analyses, a baseline survey will be designed and administered to consenting SCD patients aged 15 and older (or, for children, their carers) attending clinics at the teaching hospitals in Abuja, Lusaka, and Kumasi—"active" patients. To understand SCD care provided and perceptions of access to care and quality of care, we will sample 300 participants (either a patient or their carer) in each teaching hospital. The tool will be administered electronically by a research assistant, and built on Microsoft Forms. Responses will be password protected and automatically sent—or queued to be sent—to cloud storage depending on internet connectivity. A similar survey will be administered to individuals with SCD who do not access SCD care from the formal national health service—"inactive patients" (see Appendix 1 for *drafts* of both tools—these will likely change with scoping review/media content analysis inputs). They will be identified through snowball sampling (by peer-SCD patients) and local community-based organisations who support SCD-affected persons. This information will provide a broad understanding of the socio-cultural and health system barriers they face in accessing of SCD care.

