|                                    |               | Transportation                                    |
|                                    |               | Permission to access care                         |
|                                    |               | Other [please indicate]                           |
| 10 What do you                     |               | [Open text]                                       |
| make it easie                      |               |   |
| patients to a                      | ccess SCD     |   |
| care?                              |               |   |
| 11 Do you/your                     | dependent     | Yes   |
| face stigma of                     |               | No  |
| discriminatio                      |               | l don't know                                      |
| result of you                      | r/their SCD   |   |
| diagnosis?                         |               |   |

| 11a | [If yes to 11]          | [Open text]   |
|-----|-------------------------|---|
| IIa | Please explain why you  |   |
|     | stated yes              |   |
|     | Stated yes              |   |
| 12  | Do you feel that there  | Yes   |
|     | are misconceptions      | No  |
|     | about SCD in your       | I don't know  |
|     | community?              |   |
| 12a | [If yes to 12] What do  | [Open text]   |
|     | you think those are?    |   |
|     |                         |   |
| 40  | Trung of some provided  | Coloct of that any bi   |
| 13  | Type of care provided   | Select all that apply   |
|     | today                   | Counselling   |
|     |                         | Pain management   |
|     |                         | Blood transfusion
Prevention of infection                                  |
|     |                         | Vaccinations  |
|     |                         |   |
|     |                         | Mental health/psychosocial support
Treatment for chronic organ dysfunction |
|     |                         | Hydroxycarbamide/hydroxyurea  |
|     |                         | Stem cell therapy   |
|     |                         | Other [Please indicate]   |
|     |                         | I don't know  |
|     |                         | Nothing   |
| 14  | Types of care received  | Select all that apply   |
| '-  | to-date                 | Counselling   |
|     |                         | Pain management   |
|     |                         | Blood transfusion   |

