# Situational Analysis: Patient Survey: Inactive Patients

|     | Prompt  | Response   |
|-----|---|--|
| 1   | Date  | [dd/mm/yy]   |
| 2   | Participant ID  | [######]   |
| 3   | Country   | Ghana
Nigeria
Zambia   |
| 4   | Participant/ dependent age at last birthday   | [Age in years]   |
| 5   | Participant/ dependent age of SCD diagnosis   | [Age in months—e.g. three years = 36 months]   |
| 6   | Do other members of
your family have SCD?  | Yes [number]
No
I don't know   |
| 7   | Number of health
facilities at which SCD
care has been sought   | 1
2–3
4–5
More than 5
I don't know
N/A—I have never sought care at a health facility      |
| 8   | Do you feel that it is
important to receive care
for SCD?   | Not at all important
Somewhat important
Very important
Not sure                                 |
| 9   | [If "not at all important",
"somewhat important",
or "very important" to 8]
Can you please explain
why you feel that it is/is
not/is somewhat
important to receive SCD
care? | [Open text]  |
| 10  | Why are you/your
dependent not
undertaking care for
SCD?   | Select all that apply
Costs
Transportation
Permission to access care
Other [please indicate] |
| 11  | What do you feel would
make it easier for
patients to access SCD
care?   | [Open text]  |
| 12  | Do you/your dependent
face stigma or
discrimination as a
result of your/their SCD
diagnosis?  | Yes
No
I don't know  |
| 12a | [If yes to 12]
Please explain why you
stated yes  | [Open text]  |

| 40  | De yey feel that the    | Vee                                     |
|-----|-------------------------|---|
| 13  | Do you feel that there  | Yes                                     |
|     | are misconceptions      | No                                      |
|     | about SCD in your       | l don't know                            |
|     | community?              |   |
| 13a | [If yes to 13] What do  | [Open text]                             |
|     | you think those are?    |   |
|     |                         |   |
|     |                         |   |
| 14  | Have you/your           | Yes                                     |
|     | dependent ever received | No                                      |
|     | care for SCD?           | l don't know                            |
|     |                         |   |

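### The draft closed barrier list offers no health-system option, although the survey is meant to describe health-system barriers

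*Protocol*

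**What the plan says.** Protocol section 3.3 (Baseline patient survey) describes a survey of active patients and a similar one for people with SCD outside formal care, and closes: "This information will provide a broad understanding of the socio-cultural and health system barriers they face in accessing of SCD care". It calls both tools drafts and says that "these will likely change with scoping review/media content analysis inputs".

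The response options for item 10 of the inactive form, which asks why care is not being taken up, are: "Select all that apply Costs Transportation Permission to access care Other [please indicate" (a free-text field). Item 9a of the active form has the same three named options and 'Other', but is asked only after a 'Yes' to item 9, whether the respondent faces barriers.

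Both forms ask elsewhere about stigma ("Do you/your dependent face stigma or discrimination as a result of your/their SCD diagnosis") and about community misconceptions, each with an open follow-up.

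A footnote in section 3.3 says the work on social factors "this will be complemented by research into geographical and financial factors that are part of an epidemiological and mapping study".

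Section 3.4 plans descriptive statistics for the closed items and thematic coding of open text. Section 3.3 says the survey will help brief the PAC and SBA teams, and that the pooled situational-analysis findings will inform their priority topics.

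**The concern.** The survey has two declared targets, socio-cultural barriers and health-system barriers. The one item that yields a percentage per barrier has no named option for the second. A medicine stock-out, a blood shortage or mistrust of the service must be raised unprompted, while cost, transport and permission are on the list. Answers collected in these two ways are not comparable as frequencies.

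The facility teams work on the supply side of care, which is the part the list leaves out. If the briefing shows cost and transport with sizeable percentages and supply problems as a scatter of 'Other' entries, the teams could take a feature of the form for a feature of the patients.

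**Working it through.** No figure in the plan needs reproducing. The check is a count of response options and items on the two Appendix 1 forms, set against the stated aim.

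**1. The closed list (active 9a, inactive 10).** Three named options plus 'Other'. Costs is financial, transportation arguably geographical, permission socio-cultural. Health-system options: 0 of 3.

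**2. Other items that could record a barrier.**

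| | Active form | Inactive form |
|---|---|---|
| Closed socio-cultural items outside the list | 2 (items 11, 12) | 2 (items 12, 13) |
| Closed items on quality of care | 2 (items 15, 17) | 0 |
| Open items where a health-system barrier could be volunteered | items 10, 16, 17a | items 9, 11, 15 |

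The inactive form therefore has no closed health-system or quality item. Inactive patients are also the nearest group to which the aim sentence refers. The stigma and misconception items ask whether these exist, not whether they are a reason for not using care, so they cannot be tallied beside cost. On the active form, the routing note for item 17a points to item 16, which is open text; the yes/no parent is item 17. If built as written, that open item may not be triggered.

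**3. Denominators.** Table 1 plans 900 active and 300 inactive respondents: 900 + 300 = 1,200. Section 3.5 allows the inactive number to fall. Item 10 goes to every inactive respondent; item 9a goes only to the unknown fraction of active respondents who answer 'Yes' to item 9. Someone who does not think of a shortage or a long wait as a barrier never reaches the list. The two groups' percentages therefore have different bases.

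**4. Direction of the bias.** Let p be the share who would select a barrier if it were named, and v the fraction of them who volunteer it when it is not. The recorded share is p × v, against p for an equally common named barrier. With v = 1 nothing is lost; with v = 0.5 the recorded share is half; with v = 0.25 it is a quarter. These values of v are assumptions for illustration, as the document gives none. Any v below 1 produces an under-count.

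**5. Does the protocol already supply candidate options?** Section 1.1 mentions blood shortages and mistrust of the health system, in explaining how blood is used in SCD. Section 1.2 mentions the difficult move from paediatric to adult clinics. Section 3.3 (Phase 2, Realist evaluation) lists availability of medicines or equipment as contextual data to monitor.

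**The case against.** The strongest reply is that the forms are placeholders. The scoping review of barriers runs in months 6–12 and the survey in months 12–15 (section 4), so its results can shape the final list. Section 5.7 then requires piloting to confirm that responses are exhaustive. This lowers the severity. But nothing commits the revision to health-system options or to removing the item 9 filter, and a list with 'Other' passes a test of exhaustiveness as it stands.

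Second, other barriers can still be reported. Open items on both forms are coded thematically, the item 9 filter gates only 9a, and patient and carer focus groups ask about barriers directly. This stands: the information is not lost. What is lost is a frequency comparable with the named options, which three focus groups per country cannot supply.

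Third, the survey is administered by a research assistant, and the protocol does not say whether options are read aloud. If they are not, the prompting effect may be smaller. This too stands as a limit on the size.

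Two stronger readings are tempting and are not supported. A reader might infer that the form fixes a ranking of barriers. The protocol plans no ranking from the survey: PAC teams rank barriers themselves (section 2.1), and SBA teams do their own root cause analysis (section 2.2). A reader might also infer that cost and transport belong to the separate epidemiological and mapping study and should not be here. The footnote says only that the work is "complemented by research into geographical and financial factors that are part of an epidemiological and mapping study", and section 1.2 itself names economics and geography among the factors that limit access. Both options are in scope and should stay.

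**Conclusion.** The point holds in a limited form. The draft list has 0 health-system options among 3 named ones, against an aim that names health-system barriers explicitly. The gap is widest on the inactive form, which has no closed item on the subject; on the active form, item 9 narrows who sees the list. Tallies from 9a and 10 will probably under-count health-system barriers relative to costs, transportation and permission. This rests on the assumption that some respondents who would select a named option will not volunteer it. The size is unknown. Up to 1,200 respondents are planned, though not all active ones would reach 9a. Because the forms are drafts and the survey is exploratory, this is a worthwhile correction to the instrument and not a flaw in the study design.

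**What to change.** Make the change when the drafts are revised after the scoping review and before piloting.

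- Keep costs, transportation, permission and 'Other'.
- Add to both forms one common set of health-system and social options drawn from the protocol and the scoping review: for example, medicines, blood or equipment not available; mistrust of the health service; stigma; difficulty moving from paediatric to adult clinic.
- Ask the list of every active respondent, not only those answering 'Yes' to item 9.
- Report active and inactive patients on the same list, each with all respondents in that group as denominator. Note that the questions differ: barriers faced on one form, reasons for not taking up care on the other.
- State whether the options are read aloud, and correct the routing of item 17a.

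If the list is not extended, say in the analysis section and in the team briefing that tallies from 9a and 10 do not show the relative importance of barriers.

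The cost is edits to two draft forms and a slightly longer interview. Section 3.5 caps the active survey at 30 minutes, so the pilot should confirm that the longer list fits.
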